8.3.4 Additional Analyses of the Primary Efficacy Endpoint(s)

A line graph by treatment group of the LS means with 95% confidence intervals derived from the primary MMRM model will be produced.

The analysis of the primary endpoint will be repeated based on the MMIAS.

The NIHSS total score will be summarized continuously at Baseline and each visit including Post-Treatment with the number of observations, mean, standard deviation, minimum, Q1, median, Q3, and maximum.

The change from baseline in the NIHSS total score will be summarized based on the MMRM noted in Section 8.3.3. Change from baseline to specified time points (Day 2-4, Week 4, Week 8, Week 12, Week 24, Week 36, Week 52) will be derived from a contrast of the group-level least squares (LS) means. The visit means, standard error, and 95% confidence interval, as well as the between-group difference, standard error, 95% confidence interval, and effect size will be presented for each visit during the Treatment Period.

The number and percentage of responders for the NIHSS total score will be summarized based on a responder definition of improvement (decrease) from Day 1 of at least 4 points

and at least 8 points improvement at visits Day 2-4, Week 4, Week 8, Week 12, Week 16, Week 20, Week 24, Week 28, Week 32, Week 36, Week 40, Week 44, Week 48, and Week 52, as well as a responder definition of NIHSS total score ≥ 0 at the specified time point.

[figure not shown]
The plot of the cumulative distribution function of the NIHSS total score at Weeks 12, 24, and 52 will be produced based on the data as observed.

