- ✓ 7. NIHSS total score of 7 to 21, inclusive. NIHSS eligibility must be confirmed within 1 hour before randomization. For subjects treated with IV tPA \pm EVT, NIHSS must be confirmed \geq 1 hour after completion of all treatments and once any confounding effects of sedation or anesthesia have resolved.
- ✓ 8. No evidence of acute seizure at the onset of index stroke based on assessments conducted per standard of care. Subjects with evidence of seizure at onset of index stroke, but with imaging conclusively demonstrating an acute ischemic stroke are still allowed.
- ✓ 9. No evidence of acute myocardial infarction based on assessments per standard of care (e.g., elevated troponin levels, abnormal ECG).
- ✓ 10. In the judgment of the investigator, symptoms are not considered likely to resolve within the subsequent few hours (e.g., transient ischemic attack [TIA]).

Subject History

- ✓ 11. Subjects or their legally authorized representative confirms that before index stroke, there was no substantial impairment in subject's ability to perform activities of daily living (e.g., dressing, eating, walking, bathing, toileting) without assistance, as defined by a modified Rankin Score (mRS) of 0 to 2 before the index stroke.
- ✓ 12. Subjects with a history of previous stroke more than 3 months before enrollment are allowed if they are no longer experiencing ongoing functional recovery and mRS remains 0 to 2 prior to index stroke.
- ✓ 13. No known history before randomization of clinically significant medical conditions (other than current acute ischemic stroke) or any other reason, including any physical, psychological, or psychiatric condition that in the investigator's opinion would compromise the safety or interfere with the subject's participation in this study, or would make the subject an unsuitable candidate to receive study drug, or would put the subject at risk by participating in the study. Subjects with comorbid conditions that are, in the opinion of the investigator, clinically stable and not expected to meaningfully progress in the following 12 months may be considered eligible.
- ✓ 14. No known medical history of repeated episodes of complex migraine (e.g., weakness, vision, difficulty speaking). Subjects with history of complex migraine, but with imaging conclusively demonstrating an acute ischemic stroke are still allowed.

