2.2 Study Design Overview

[figure not shown]
This is a 52-week, Phase 2a, randomized, double-blind, parallel-group, placebo-controlled, multicenter proof-of concept study to evaluate the safety and efficacy of elezanumab in subjects with acute ischemic stroke.

Administration of blinded study drug must be initiated as soon as possible but no later than 6 hours after randomization and done every 4 weeks thereafter through Week 48 for a total of 13 doses. The final double-blind Treatment Period study visit will be at Week 52. Subjects will have 2 post-treatment follow-up visits at 12 and 24 weeks after last dose of study drug, and a final follow-up phone call 39 weeks (~5 half-lives) after last dose of study drug.

Final efficacy analyses will be performed after the last subject completes the Week 52 visit and after an interim database lock. Final safety analyses will be performed following completion of the post-treatment period and final database lock.

The schematic of the study is shown in [Figure 1](#).

Figure 1. Study Schematic

EVT endovascular therapy; hr(s) hour(s); IV intravenous; LKN last known normal; tPA tissue plasminogen activator; Wk week

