8.0 Efficacy Analyses

8.1 General Considerations

All efficacy analyses will be conducted in the FAS. Where noted, some analyses may additionally be conducted in the MMIAS. Because this is a small, exploratory, proof of concept study, p-values will not be presented. Where statistical models are noted, appropriate point estimates and 95% confidence intervals will be presented.

The primary analysis of efficacy endpoints will be performed after all ongoing subjects have completed the Treatment Period and an interim lock has been performed. This will be the final analysis for the efficacy endpoints during the Treatment Period.

Post treatment efficacy analyses will be completed following the final database lock.

Generally, "Baseline" refers to the last non-missing observation before the first administration of study drug. Where noted, Day 2-4 or Week 4 may be used as baseline. Unless otherwise specified, categorical variables will be summarized with the number and percentage of subjects in each category. Responder analyses will be presented with the number and percentage of subjects in each category, the difference in proportion of responders between the 2 treatment groups, and the 95% confidence interval for the difference based on Wald confidence limits, unless otherwise specified. Continuous variables will be analyzed using Mixed-Effect Model for Repeat Measures (MMRM) method. The dependent variable will be the visit value and baseline (pre-dose, Day 2-4 or Week 4, depending on the endpoint) will be included as one of the timepoints in the repeated measures. For analyses of change from baseline (pre-dose, Day 2-4 or Week 4, depending on the endpoint), this will be derived from a contrast of the group-level least squares (LS) means from the MMRM.

Unless otherwise specified, any subject who is randomized based on a wrong stratum will be analyzed according to the actual stratum the subject belongs to based on the eCRFs as noted in Section [7.2](#).

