8.2 Handling of Missing Data

Missing data will be imputed using the following methods for the efficacy analyses:

- Non-Responder Imputation (NRI): the NRI analysis will categorize any subject who does not have evaluation during a specific visit window as a non-responder for that visit. Unless otherwise noted, this will be the primary approach for accounting for missing data in responder analyses.
- Generalized linear mixed model (GLMM): The model will include a logit link function to compare the probability of having responder between treatment groups of each visit of Day 2-4, Week 4, Week 8, Week 12, Week 24, Week 36, Week 52, and will include baseline NIHSS as a covariate and time from last known normal and initiation of first dose (≤ 12 hours, > 12 hours), tPA use (Y/N), EVT use (Y/N), visit, and treatment group as fixed effects. An unstructured variance covariance matrix will be used. The compound symmetry variance covariance matrix will be used if the model does not converge with unstructured matrix. The GLMM model relies on a missing at random (MAR) assumption.
- As Observed (AO): The AO analysis will not impute values for missing evaluations, and thus a subject who does not have an evaluation on a scheduled visit will be excluded from the AO analysis for that visit. AO will include all values collected in the study.
- MMRM: The repeated measures analysis will be conducted using a mixed model including observed measurements at all visits. The mixed model includes the categorical fixed effects of treatment, visit and treatment-by-visit interaction, main stratification factors at randomization, and the continuous fixed covariates of baseline measurement, unless otherwise noted. An unstructured variance-covariance matrix will be used; if the model does not converge, then a compound symmetry variance-covariance matrix will be used. Denominator degrees of freedom will be computed using the Kenward-Roger method. Parameter estimation is based on the assumption of data being missing at random and using the method of restrictive maximum likelihood. MMRM will be the primary approach in the analysis of continuous

variables unless otherwise noted. The MMRM model relies on a missing at random (MAR) assumption.

For all analyses related to the mRS, if a subject has a value of 6 (dead), this will be carried forward to future visits in the analysis. This will be applied to all mRS analyses, including the responder analysis as observed.

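### The 8-point NIHSS responder row in SAP 8.3.4 cannot be met from a Day 1 score of 7, so full recovery from the lowest entry score is tabulated as non-response

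*SAP*

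**What the plan says.** Protocol 5.1, criterion 7, sets the entry range: "NIHSS total score of 7 to 21, inclusive. NIHSS eligibility must be confirmed within 1 hour before randomization".

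SAP 8.3.4 then lists three NIHSS responder summaries in one sentence:
- a "responder definition of improvement (decrease) from Day 1 of at least 4 points";
- "at least 8 points improvement at visits Day 2-4" and at the further visits up to Week 52, 14 visits in all;
- an absolute-score rule, printed "as well as a responder definition of NIHSS total score ≥ 0 at the specified time point".

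The 8-point rule has no alternative for a subject who recovers fully. SAP 8.1 says that responder analyses show the difference in proportions between arms with a 95% Wald interval unless otherwise specified, so the row carries a between-arm contrast and not only counts. SAP 8.2 makes non-responder imputation the default for responder analyses: "the NRI analysis will categorize any subject who does not have evaluation during a specific visit window as a non-responder for that visit". No p-values are planned.

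**The concern.** A change threshold of 8 points sits one point above the lowest score that the trial enrols. For a subject who starts at 7, the best possible outcome falls in the same category as no change, and under the default imputation in the same category as a missing visit. Protocol 4.2 justifies the 7 to 21 range partly on the ground that such subjects have room to show a treatment effect; on this row, subjects at 7 have none.

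Two things are at stake. Subjects who cannot respond add nothing to the numerator of either arm, which pulls the between-arm difference towards zero. And the highest attainable rate in each arm depends on how many low scorers it happens to receive, because baseline NIHSS is not a stratification factor and the Wald interval is unadjusted. The study is exploratory and has no type I error control, so supportive rows of this kind form part of the pattern from which it will be read.

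**Working it through.** **Inputs.** Entry scores 7 to 21, which is 15 integer values (Protocol 5.1). Thresholds of 4 and 8 points from Day 1 (SAP 8.3.4). About 120 subjects, 1:1, so 60 per arm (Protocol synopsis). Assumed, because the visible text does not state it: the scale floor is 0. The documents give no expected responder rate, so there is no planned figure to reproduce.

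**Attainability.** The largest possible fall from Day 1 score b is b − 0 = b. The 8-point rule needs a visit score of b − 8 or lower.

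| Day 1 score | Largest fall | Visit scores that meet the 8-point rule | Added by an alternative of 0 | Added by an alternative of 0 or 1 |
|---|---|---|---|---|
| 7 | 7 | none (−1 needed) | 0 | 0, 1 |
| 8 | 8 | 0 | none | 1 |
| 9 | 9 | 0, 1 | none | none |
| 21 | 21 | 13 or lower | none | none |

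So 1 of the 15 entry scores can never meet the rule. An alternative of 0 brings this to 0 of 15. The 4-point rule needs a score of 3 or lower from 7 and is attainable from every entry score.

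**Share of subjects affected (assumptions).** Let q be the share with a Day 1 score of 7. The 8-point rate cannot exceed 1 − q.
- Uniform over 7 to 21: q = 1/15 = 6.7%; 120 × 1/15 = 8 subjects; ceiling 93.3%.
- Frequency falling 5% per point: q = 9.3%, about 11 of 120.
- Frequency falling 10% per point: q = 12.6%, about 15 of 120.
- Wider range, q = 2% to 15%: 2.4 to 18 subjects; ceiling 98% to 85%.

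**Subjects reclassified.** Let r be the share of those at 7 who reach 0, assumed 20% to 60%. The number moved from non-responder to responder by an alternative of 0 is 120 × q × r.
- Uniform: 8 × 0.2 = 1.6 to 8 × 0.6 = 4.8 subjects, or 1.3 to 4.0 percentage points of the pooled rate.
- q from 2% to 15%: 2.4 × 0.2 = 0.5 to 18 × 0.6 = 10.8 subjects, or 0.4 to 9.0 points.

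An alternative of 0 or 1 also moves subjects who go from 7 to 1 and from 8 to 1. The documents give no basis for counting them.

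**Dilution.** If the effect on the responder rate would otherwise be the same at every score, the observed difference is (1 − q) times that effect: a relative loss of 6.7% in the uniform case, and 9.3% or 12.6% in the two skewed cases.

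**Chance imbalance.** Suppose that 12 subjects have a score of 7 and split 8 v 4. With 60 per arm, a split at least that uneven has a probability of about 36% (hypergeometric). The ceilings are then 52/60 = 86.7% and 56/60 = 93.3%. The expected shift in the observed difference is smaller: (8 − 4)/60 × 0.2 to 0.6 = 1.3 to 4.0 points. For scale, the standard error of a difference at a 50% rate is √(2 × 0.25/60) = 9.1 points.

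**The case against.** The strongest reply is about consequence, and most of it stands. The row belongs to the additional analyses. The primary analysis uses the NIHSS scores themselves through the MMRM-based AUC and so takes in a fall from 7 to 0 in full. The secondary endpoint is mRS 0 to 2 at Week 52. No decision rule uses the 8-point count. The same section also gives continuous summaries, change from baseline by visit, and cumulative distribution plots at Weeks 12, 24 and 52. A pure change threshold is a legitimate choice, and the 8-point row can be seen as the upper of two tiers.

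A reader might infer three stronger things that the documents do not support.
- *That full recovery is counted as treatment failure.* The SAP does not use that term, and a subject who goes from 7 to 0 is a responder on the 4-point rule in the same sentence.
- *That 86.7% v 93.3% is a gap to expect in the results.* Those are ceilings, reached only if every other subject responds.
- *That subjects with Day 1 scores below 7 enlarge the excluded group.* Dosing may start "no later than 6 hours after randomization" and baseline "refers to the last non-missing observation before the first administration of study drug", so a later and lower score is possible. The visible text does not show that the NIHSS is repeated between eligibility and dosing. If it is not, nobody is below 7.

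It can also be said that the absolute-score rule already captures full recovery. That depends on the printed sign. As printed, a score of 0 or more is met by every scored subject and tells the reader nothing. If the intended sign is equality, full recovery has its own row, but the 8-point row is still capped.

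**Conclusion.** The point holds as a definitional flaw in one descriptive row. A Day 1 score of 7 can never give an 8-point response, and a score of 8 gives one only at exactly 0. The result is misclassification of some full recoveries, with modest dilution and chance imbalance. It is not systematic bias, since the ceiling applies to both arms and nothing in the documents suggests that it favours one of them.

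In the uniform case, 8 of 120 subjects could never respond, and 1.6 to 4.8 of them would be reclassified if 20% to 60% reach 0. These sizes rest on an assumed baseline distribution, an assumed recovery share and a scale floor of 0; the attainability result needs only the floor. No primary or secondary result changes.

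**What to change.** In SAP 8.3.4, define the 8-point responder as a decrease from Day 1 of at least 8 points, or an NIHSS total score of 0 or 1 at the visit. At minimum, credit a score of 0, which makes the rule attainable from all 15 entry scores. Keep the strict 8-point count as a supportive row. Leave the 4-point definition unchanged: reaching 0 or 1 from 7 or more is already a fall of at least 6, so the clause would change nobody in the entry range.

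The cost is one sentence and one line of derivation code, with no new data. The small downside is that the composite mixes change with final state, which the strict row offsets. The change should be made before unblinding, because a later redefinition would be less credible.

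Separately, check the adjacent absolute-score rule, printed as a total score of 0 or more, against the source file. It may be a text-extraction error; if the sign is really there, it needs correcting.

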2.3 Treatment Assignment and Blinding

Subjects will be randomized to elezanumab or placebo in a 1:1 ratio. Randomization will be stratified by intravenous (IV) tissue plasminogen activator (tPA) use (yes/no), treatment with endovascular therapy (EVT) (yes/no), and by time since "last known normal" (\leq 11 hours or $>$ 11) at the time of randomization.

The primary analysis of efficacy endpoints will be performed after the last subject completes the Week 52/Premature discontinuation visit. At this time, an interim database lock will occur, the randomization will be loaded into the database and the Data and Statistical Sciences department at AbbVie will perform the statistical analysis. Final safety analyses and post-treatment efficacy analyses will be performed following completion of the post-treatment period and database lock.

Study sites and subjects will remain blinded through the duration of the study.

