2.4 Sample Size Determination

The primary efficacy endpoint is the monthly-adjusted, model-based area under the curve (AUC) of the National Institutes of Health Stroke Scale (NIHSS) total score during the Treatment Period. Approximately █ subjects will be randomized to elezanumab █ mg or placebo in a █ ratio. Assuming the true difference in AUC is █, this sample size is sufficient to show a █ difference in AUC (with the elezanumab group having a lower, i.e., better, AUC) between treatment and placebo with a posterior probability of > █%. This sample size was calculated based on simulations and included a █% mortality rate for the population under █ years of age, █% mortality rate for the population greater than or equal to █ years of age, and an additional █% discontinuation rate.

The number and proportion of missing assessments (due to missed visits or study drug discontinuation) will be monitored on an ongoing basis and if the proportion of missing assessments is higher than planned, additional subjects may be randomized.

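### As supplied, SAP 8.3.4 counts an NIHSS total score of 0 or more as a response, which every eligible patient already meets before dosing

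*SAP*

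**What the plan says.** SAP 8.3.4 plans three NIHSS responder summaries. Two rest on change: "improvement (decrease) from Day 1 of at least 4 points", and a stricter version requiring 8 points. The third rests on the absolute score: "as well as a responder definition of NIHSS total score ≥ 0 at the specified time point".

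Three other places bear on how the third rule works:

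- **Direction of benefit.** The change rules treat a decrease as improvement, and SAP 2.4 describes the hoped-for result "with the elezanumab group having a lower, i.e., better, AUC".
- **Entry range.** Protocol 5.1 requires "NIHSS total score of 7 to 21, inclusive. NIHSS eligibility must be confirmed within 1 hour before randomization". The synopsis gives the same range.
- **Reporting and missing data.** SAP 8.1 says responder analyses will show counts and percentages, "the difference in proportion of responders between the 2 treatment groups, and the 95% confidence interval for the difference based on Wald confidence limits". SAP 8.2 describes a non-responder imputation that will "categorize any subject who does not have evaluation during a specific visit window as a non-responder for that visit", and adds: "Unless otherwise noted, this will be the primary approach for accounting for missing data in responder analyses".

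The absolute-score rule is not restated anywhere else in the visible text, so no other section shows which operator or cut-off was meant.

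**The concern.** A responder rule on a scale where low is good needs an upper limit. The printed rule sets a lower limit, and that limit lies below the whole entry range. It therefore cannot separate patients who recovered from patients who did not.

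It also disagrees with the other two rules in its own sentence. A patient who enters at 21 and is still at 21 at Week 52 fails both change rules and passes this one.

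At stake is one table. If it were programmed literally, its rows would be headed as NIHSS response and would carry a between-arm difference with an interval, yet would contain no information on neurologic recovery.

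**Working it through.** The plan states no rate or power figure for this rule, so there is nothing of its own to reproduce. The check is logical, with a short illustration.

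**Inputs.** Rule: total score ≥ 0 (SAP 8.3.4). Entry range: 7 to 21 inclusive (Protocol 5.1 and synopsis). Planned size: about 120 randomized 1:1 (Protocol 4.2), so 120 / 2 = 60 per arm, used only in step 4.

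**Step 1: entry scores.** Taking totals as whole points, the range holds 21 − 7 + 1 = 15 values.

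- Meeting ≥ 0: 15 of 15, or 100%.
- Meeting any upper limit below 7: 0 of 15.

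This step needs no assumption about the limits of the scale. Every eligible patient is a responder at the eligibility assessment.

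**Step 2: a patient who does not improve.** Entry 21, follow-up 21: decrease = 21 − 21 = 0. The 4-point rule fails (0 < 4), the 8-point rule fails (0 < 8), and the absolute rule passes (21 ≥ 0). The same holds for any increase from entry.

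**Step 3: as-observed rate at follow-up.** Assume totals cannot be negative. Every assessed patient then passes, so both proportions equal 1.

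- Difference: 1 − 1 = 0.
- Wald standard error: √(1 × 0 / n₁ + 1 × 0 / n₂) = 0.
- 95% interval: 0 to 0, whatever the arm sizes.

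**Step 4: rate if the non-responder default applies.** With every assessed patient passing, the rate in each arm is the number assessed divided by the number in the arm. As an illustration, take 60 per arm with 20% of visits missing on elezanumab and 10% on placebo. Both missing rates are assumed, not taken from the documents.

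- Rates: 1 − 0.20 = 0.80 and 1 − 0.10 = 0.90; difference −0.10.
- Standard error: √(0.80 × 0.20 / 60 + 0.90 × 0.10 / 60) = √0.004167 = 0.0645.
- 95% Wald interval: −0.10 ± 1.96 × 0.0645, or −22.7 to +2.7 percentage points.

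Swapping the two missing rates gives +10 points (−2.7 to +22.7). Equal missingness of 10% gives a difference of 0 (−10.7 to +10.7). In every case the contrast describes attendance and nothing else.

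**The case against.** The strongest objection is that the point hangs on one character in machine-read text. That text has visible faults. The SAP's Figure 1 footnote has lost the equals signs that the protocol's version keeps, the protocol spells the product name in two ways, and a marker for missing content follows the sentence in SAP 8.3.4. A rule that contradicts the direction of benefit in its own sentence is what a misread symbol would produce.

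This limits confidence but does not dispose of the point. The only fault shown for an equals sign is loss, not conversion to ≥. Inequality signs elsewhere in the SAP (7.2, 8.3.3, 8.6) read sensibly, and an equals sign survives in the text of 8.3.3. The documents cannot settle whether the fault lies in the reading or the drafting.

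A second objection is that the missing-data method for these rates is uncertain. This stands. The visible text of 8.3.4 names no method, which points to the non-responder default, but content nearby is hidden. SAP 8.2 also describes a logistic mixed model for responders that includes Day 2-4 and baseline NIHSS, unlike the mRS model in 8.4, so it may be meant for another endpoint. A reader might infer that non-responder imputation definitely governs this table; the documents do not establish that.

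A third objection is that little would be lost. This largely stands. No p-values are planned, the summary is descriptive, and a rate of 100% at every visit would probably be noticed when the tables were first run. The cumulative distribution plots would still show as-observed shares at low scores at Weeks 12, 24 and 52, although not an imputed rate or a between-arm interval.

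**Conclusion.** The point holds as a query to verify and then correct. The rule as supplied cannot work as a responder definition: all 15 eligible entry scores meet it before dosing, and patients who fail to improve or worsen continue to meet it. That much follows from the documents, taking scores as whole points. The 100% as-observed rate in both arms further assumes a scale without negative totals. The reading of the rate as the share assessed further assumes that the non-responder default applies.

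Severity is minor, and confidence is low to medium because the operator is unconfirmed.

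Two stronger readings should be resisted. A reader might infer that the efficacy conclusions are compromised. They are not: the primary AUC, the mRS secondary endpoint and the 4- and 8-point rules do not use this definition. A reader might also infer that the intended rule was a score of exactly 0. The documents never give that cut-off, and other upper limits would fit equally well, so no corrected rate can be computed.

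**What to change.** Compare the operator in SAP 8.3.4 with the approved SAP. If the approved text already has a cut-off in the improving direction, nothing needs to change.

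If ≥ 0 is genuine, replace it with the sponsor's intended cut-off, expressed as an upper limit below the entry range (below 7). Do this before the point described in SAP 2.3, when "an interim database lock will occur, the randomization will be loaded into the database". A cut-off chosen after treatment assignments are available would be post hoc and should be labelled so.

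The cost is a check of one character and, at most, one line of SAP wording. The primary model and the AUC calculation need no change in either case.
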